Using the Zoom App, participants will be invited to watch the Baduanjin mind-body exercise demonstration videos which explains how to perform the exercise movements where the instructor will explain and demonstrate the eight movements and natural breathing methods with the participants. This is done before commencing the first exercise session in the program.

In addition to self-guided practice, the participants will be asked to join in a coached Zoom exercise program with an instructor, either in the morning or afternoon or both sessions at their own choice throughout the intervention period (8 weeks). Participants will be requested to practice Baduanjin mind-body exercise at least 2 sessions per day, 6 days per week with each session lasting about 15 mins for 8 weeks. Missed sessions will not be considered as a protocol deviation.

The Baduanjin mind-body exercise sessions via Zoom are instructed by members of the research team who have at least two years' experience in the practice of Baduanjin mind-body exercise. If participants miss out on any Zoom sessions, they can watch the demonstration video as a reference. Participants will be asked to record their daily Baduanjin mind-body exercise schedule in the Exercise Logbook. Recording this in the Exercise Logbook will take approximately 2 minutes each session. This will happen twice daily, 6 times per week for 8 weeks. Weekly telephone calls will be performed by a research assistant to see how the participants are progressing and engaging with the Baduanjin mind-body exercise program. The weekly phone calls will also discuss any unexpected side effects or adverse events that might be related to the exercise.

Finally, participants are asked to complete two (2) questionnaires at baseline (week 0) as part of the study intake process, and again at the end of week 4 and week 8 of the exercise program. These questionnaires are the brief fatigue inventory (BFI) and the PROMIS-29v2.0. The BFI measures fatigue. The PROMIS-29v2.0 is a patient reported outcome measure used by health services in NSW. Together, these will take 5-10 minutes to complete online and can be accessed using secure links that will be emailed to participants.

There is also the *Credibility and Expectancy Questionnaire* (CEQ) which has four questions and takes one minute to complete. Two questions are completed before entry into the study (week 0), and two at the completion of the Baduanjin mind-body exercise program (week 9).

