7. DATA SAFETY MONITORING BOARD

One of the investigators with medical qualifications will be nominated as study medical representative and another non-investigator will provide an independent review for safety on all adverse events. This person will also monitor for correctness of completion of study documentation in terms of reporting any adverse events and other trial conduct issues that may arise in terms of safety or ethical happenings.

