The *Credibility and Expectancy Questionnaire* has been modified to assess participants perspectives on the credibility of the Baduanjin mind-body exercise program for their fatigue [32]. There are four (4) questions and takes 1 minute to complete. Questions 1 & 2 are completed before randomisation about participants expectations, and questions 3 & 4 after the final Baduanjin mind-body exercise session on the credibility of their experience [33]. Each question is measured on a Likert scale of 1-9 where 9 is the most credible.

Exercise Logbook

Participants in the intervention group will be asked to record their daily Baduanjin mind-body exercise schedule in a logbook for the 8 weeks of their exercise. This takes approximately 2 minutes each day or 10 minutes a week in total. The logbook helps understand any relationship between frequency of exercise and changes in CRF scores. It additionally assists with determining feasibility with adherence rates.

Final Feedback Form (Week 9)

Participants in the intervention group will be contacted by a member of the research team to thank them for their participation and inform them the final feedback form will be the last data collection. The research team member will check the completion of final outcome

measures and ask if participants would like a copy of the study report of findings. The participant will also be asked for further feedback on the participants experiences and future changes to assist with participation and completion of the program.

Adverse Events Reporting and Management

There are weekly telephone calls with a member of the research team to check on participants engagement with the Baduanjin mind-body exercise program and discuss any exercise related expected and unexpected side effects. If present, these are reported using the Adverse Events Form. The Principal Investigator is responsible for assessing any event as meeting the adverse event criteria threshold. Participants can report any side effects of concern daily with the exercise instructors (who are also registered health care practitioners), and these will also be reported in the Adverse Events Form for the Principal Investigator to investigate and decide.

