Each intervention group participant will receive an Exercise Logbook for reporting side effects of concern related to the Baduanjin mind-body exercise program. All Serious Adverse Events (SAEs) occurring between consent and the last visit for the study are recorded in detail in the Adverse Events Form by the member of the research team who received the original report, and who also informs the Principal Investigator. All AEs that occur between the first intervention and the last intervention for the study must be recorded in detail. In case of an AE/SAE, the Principal Investigator will initiate contact with appropriate members of the participant's health care team, or as according to their health care judgement given the nature of the AE/SAE. If necessary, participants will be withdrawn from the study. Participants with SAE/AEs present at the last intervention will be followed up until resolution of the event.

The SWSHLD Ethics Committee will be notified of any AE/SEA. Regular meetings will be scheduled by the Principal Investigator to discuss the AE with hospital clinicians. Participants will be provided a 24-hour contact number for any urgent matters or concerns. The severity, expectedness and causal relationship with the intervention will be assessed for every AE reported. The number and severity of AE, as recorded on an Adverse Events Form, will be reported in adherence to the requirements of the National Health and Medical Research Council for Clinical Trials Adverse Event Reporting.

Endpoints

Key feasibility endpoints are recruitment rates, and the participation and completion of the study interventions (from Logbook data) within the stated study periods. For feasibility and contributing to the design of a larger clinical trial, the primary outcome measure endpoint

will also include the effect of Baduanjin mind-body exercise on changes of fatigue as measured by the BFI score at baseline (week 0), at 4 weeks (mid-point), 8 weeks (final week) and 9 weeks (1 week follow-up) [29] (Additional secondary outcome measure endpoints will be the PROMIS-29v2.0 [28] and reported adverse events at baseline (week 0), 4 weeks, 8 weeks and 9 weeks (1 week follow-up) (Appendix 1. & Figure 1.) Participant's credibility and expectation ratings are compared prior to study group randomisation with their credibility scores on completing the Baduanjin mind-body exercise program.

Data analysis

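### Routine prompts for non-serious adverse events ask only about exercise-related ones, which is narrower than the protocol's rule that all AEs be recorded and independently reviewed

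*Protocol*

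**What the plan says.** **What must be recorded.** Section 10 of the Protocol (Adverse Events Reporting and Management) sets a rule without a causal limit: "All AEs that occur between the first intervention and the last intervention for the study must be recorded in detail". Attribution comes later: "The severity, expectedness and causal relationship with the intervention will be assessed for every AE reported". Serious events are to be recorded from consent to the last visit, also whatever their cause. Section 7 adds that "another non-investigator will provide an independent review for safety on all adverse events".

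**What is asked during the 8 weeks.**
- Weekly call, Section 10: staff will "discuss any exercise related expected and unexpected side effects".
- Weekly call, Section 5.8: the calls will "discuss any unexpected side effects or adverse events that might be related to the exercise".
- Telephone check-ins, Section 6.1: their purpose is to watch for harms connected with the study.
- Logbook, Section 10: each intervention participant "will receive an Exercise Logbook for reporting side effects of concern related to the Baduanjin mind-body exercise program".

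**What happens to a report.** Side effects that are present go on the Adverse Events Form. Section 10 then says: "The Principal Investigator is responsible for assessing any event as meeting the adverse event criteria threshold". The criteria are not given.

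**Where it counts.** The number and severity of side effects or AEs is secondary outcome (c) in Section 10. Safety is part of the secondary objectives in Section 3, which look ahead to a larger trial.

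**The concern.** The recording rule and the prompts that feed it have different scopes. The rule expects every event to be written down and its cause judged afterwards. The prompts ask the participant, or the research assistant on the phone, to make that judgement first.

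This matters in this population because participants may be on chemotherapy. Section 6.2 lists dizziness, drowsiness, nausea and vomiting among reactions reported with this exercise, and a participant could readily ascribe any of these to cancer treatment. If that happens before the call, a question about exercise-related effects gives no reason to mention the symptom. The formal causality assessment then never reaches it, since it applies only to events that were reported. The independent reviewer cannot review an event that nobody wrote down.

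What is at stake is the completeness of a secondary outcome that is meant to inform the design of a larger trial.

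**Working it through.** The plan gives no figure on this point, so the check compares the texts and counts contacts.

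**Step 1. Scope of each route for non-serious events, intervention group.**

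| Route | Where | Limited by attribution? | Solicited or volunteered |
|---|---|---|---|
| Weekly call | Section 10 | Yes: exercise-related | Solicited |
| Weekly call | Section 5.8 | Yes, but wider: possibly related | Solicited |
| Telephone check-in | Section 6.1 | Yes: study-related | Solicited |
| Logbook side-effect record | Section 10 | Yes: related to the programme | Solicited (written) |
| Logbook warning-symptom instruction | Section 6.2 | No: triggered by the symptom | Volunteered |
| Report to an instructor | Section 10 | No explicit limit, though it speaks of side effects | Volunteered |
| Week 9 call | Section 5.8 | No | Solicited |

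All routine prompts in weeks 1 to 8 carry a causal qualifier. The routes without one are either volunteered or come after the exercise has ended.

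**Step 2. Count of scheduled contacts.** Appendix 1 marks AE assessment for the intervention group in weeks 1 to 9, which is 9 contacts. Section 5.8 budgets 5 minutes a week and 40 minutes in total for check-ins, and 40 / 5 = 8 calls. So 8 of 9 contacts use the limited prompt and 1 of 9 is open. With 20 participants planned in the group, that is 20 × 8 = 160 limited calls against 20 × 1 = 20 open ones. The open call comes a week after the programme ends and must rely on recall of events up to about eight weeks old.

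**Step 3. Compare with the rule.** The set the rule requires is all AEs from first to last intervention. The set the weekly prompts request is the part thought to be, or possibly be, related to the exercise. The second set lies inside the first. The difference is non-serious events attributed elsewhere, and these have no solicited route until week 9.

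**Step 4. The Principal Investigator's decision.** In Section 10 the form is completed first and the decision is described after it. The undefined threshold concerns whether something is an adverse event. Causality is a separate assessment. The text does not say what becomes of an entry judged to fall below the threshold, nor at what point the medical representative and the independent reviewer of Section 7 receive the forms.

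**Step 5. Control group.** Appendix 1 marks AE assessment for the intervention group only, so there is no comparison count against which under-recording could be seen.

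**The case against.** The strongest reply is that the recording rule already governs. All AEs and all SAEs must be recorded, whatever the calls ask, and several routes sit outside the attribution limit. The week 9 call is open. Instructors, who are registered practitioners, take reports daily. Under Section 6.2 the Logbook tells participants to inform the team of warning symptoms. The Handbook's warning signs in that section include dizziness, shortness of breath, nausea and vomiting, so the symptoms most easily blamed on chemotherapy have a trigger that does not depend on cause. Section 5.8 also speaks of possible relation, which is wider than Section 10. Records are audited weekly (Section 6.3), the independent person checks AE documentation (Section 7), and the ethics committee is notified of AEs (Section 10).

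Most of this stands, and it narrows the gap. It does not close it. A rule to record everything cannot be met by prompts that ask for less. Audit and documentation checks act on what was written down. Apart from the week 9 call, the wider routes depend on the participant speaking up. Milder effects that Section 6.2 itself names, such as drowsiness or muscle soreness and stiffness, are not among the Handbook warning signs quoted there.

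A reader might go further and infer that the Principal Investigator's threshold filters events on causality, so that the independent reviewer sees a pre-selected set. The documents do not support this. The form comes first, the threshold is not said to test causality, and nothing says that entries are removed or withheld. A reader might also infer that events judged unrelated never reach the form. The protocol requires the opposite; under-recording is a foreseeable result of the prompts and not a stated rule.

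**Conclusion.** The inconsistency is real and should be corrected. In weeks 1 to 8 the routine prompts for non-serious events are limited by attribution in Sections 5.8, 6.1 and 10, while Sections 10 and 7 promise recording and independent review of all AEs. If the prompts are followed as written, non-serious events ascribed to cancer or chemotherapy may be missed. Serious events are not affected. The undefined AE criteria and the unspecified path to the Section 7 reviewers are lesser gaps in the same workflow.

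The size can be stated only as exposure: 8 of 9 scheduled contacts per intervention participant. It is tempting to multiply an assumed symptom rate by 20 participants, but the documents give no background rate and no share captured by the other routes, so the result would only restate the assumptions. The systematic review in Section 6.2, where 2 of 22 trials with AE protocols reported possibly caused events, is no benchmark either, since it counts trials and not events. Nor can one say that the exercise will look safer than it is, only that the count is open to that bias.

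The conclusion assumes that call scripts and the Logbook follow the protocol's wording. The Logbook is a separate file and was not available.

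**What to change.** 1. Reconcile Sections 5.8, 6.1 and 10 around one open question at each existing call and in the Logbook, for example: any new or worsening health problem since the last contact?
2. Enter every positive answer on the Adverse Events Form, and assign causality afterwards as Section 10 already provides.
3. State the AE criteria, and say that the Principal Investigator's assessment is added to the entry and does not remove it.
4. State that all forms go to the medical representative and the independent reviewer named in Section 7.
5. Ask the control group the same question at its existing calls, or report the all-cause counts as uncontrolled. If controls are asked, settle the call schedule first. Section 5.8 budgets weekly control check-ins, while Appendix 1 marks them only at weeks 0, 4, 8 and 9, and counts collected over different recall intervals would not be comparable.

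The cost is rewording of the protocol paragraphs, the call script and a Logbook page, plus a few extra minutes per call, using roles and contacts that already exist. The downside is that more unrelated events will be recorded. Without control data, the background symptoms of cancer and chemotherapy in those counts could not be separated from effects of the exercise. No clinical management needs to change.

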3. STUDY AIMS/OBJECTIVES

The primary study aim is to assess the feasibility and acceptability of a randomised controlled trial of a remotely delivered program of Baduanjin mind-body exercise with participants diagnosed with any type and stage of cancer and receiving or who have received chemotherapy, and who have identified as having CRF. Remote delivery refers to providing the program over the internet and using the video conferencing software Zoom.

The secondary objectives are to determine the effectiveness and safety of the remotely delivered Baduanjin mind-body exercise program for CRF, with consideration to the design of a larger scale clinical trial. The long-term goal is to contribute to the evidence base of interventions for CRF and improve the quality-of-life outcomes for people living with CRF.

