- Screening and recruitment phone call: 30 minutes (in week 0)
- Information session (Zoom): 30 minutes (in week 0)
- Baduanjin mind-body exercise routine: approximately 30 minutes per day or 3 hours per week; (24 hours in total spaced across weeks 1 to 8)
- Completion of Exercise Logbook: approximately 10 minutes per week (1 hour and 20 minutes in total, spaced across the 8 weeks of the Baduanjin intervention)
- Telephone weekly check-ins: approx. 5 minutes per week (40 minutes in total)
- Outcome measures: 5-10 minutes each time (in week 0, week 4, week 8, and week 9) (Approximately 20 – 40 minutes in total) and
- Final week telephone call: 5- 10 minutes (in week 9)

Control Group (2 hours)

- Screening and recruitment phone call: 30 minutes (in week 0)
- Telephone weekly check-ins: approx. 5 minutes per week (40 minutes)
- Outcome measures: 5-10 minutes each time (in week 0, week 4, week 8, and week 9) (Approximately 20 – 40 minutes in total)
- Final week telephone call: 5- 10 minutes (in week 9)

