10. RESEARCH OUTCOMES

Primary outcome

Feasibility

- a). Recruitment rate: number of enquiries and number of enrolments per month of active recruitment; or
- b). Percentage conversion to enrolment measured as participants (n) enrolled / the total number of enquiries; and participants (n) enrolled / people (n) potentially eligible.
- c). Retention rate: participants (n) completing 8-week intervention (96 sessions) and outcome measures/ participants (n) enrolled.
- d). Adherence rate: participants (n) completing at least 80% or 10 out of 12 Baduanjin mind-body exercise days per week / total participants (n) allocated to the intervention group.

Secondary Outcomes (this will be done for calculating power for a larger study)

- a) Change (reduction) in the severity of cancer-related fatigue symptoms measured by the *Brief Fatigue Inventory* (BFI).
- b) Change (reduction) in any of health domains in physical function, fatigue, pain interference, depressive symptoms, anxiety, ability to participate in social roles and activities, and sleep disturbance measured by *PROMIS–29 Profile v2.0*.
- c) The number and severity of reported side effects and / or adverse events.
- d) Participant's perceptions of the Baduanjin (mind-body exercise) program before

randomization and after completion of the program as measured by the (modified) *Credibility and Expectancy Questionnaire*.

Outcome Measurements

Brief fatigue inventory (BFI)

The brief fatigue inventory is a validated measure sensitive to assessing patient reported fatigue [29]. It comprises nine items measured on a ten-point scale that assesses the severity of fatigue and its effects on the participant's ability in activities of daily living. A global fatigue score is calculated by averaging the score of the items. The BFI is short and easy to use (approximately 5 minutes to complete).

PROMIS-29 Profile v2.0

The Participant-Reported Outcomes Measurement Information System (PROMIS-29) v2.0 profile assesses pain intensity using a single 0–10 numeric rating item and seven health domains, (physical function, fatigue, pain interference, depressive symptoms, anxiety, ability to participate in social roles and activities, and sleep disturbance), using four items per domain [30]. It assesses health intervention impacts and tracks changes in health overtime [31]. It is a standard outcome reporting tool used in NSW Health.

Credibility and Expectancy Questionnaire

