12. APPENDICES

1. Study Assessment Time-points

		Week 0 (Baseline)	Week 1	Week 2	Week 3	Week 4	Week 5	Week 6	Week 7	Week 8	Week 9 (Follow-up)
PIS and Consent	X										
Information phone call	X										
Screening (inclusion/exclusion)	X										
Consent & Enrolment		X									
Randomisation		X									
Information pack		I									
Baduanjin Zoom		I	I	I	I	I	I	I	I	I	
AE Assessment			I	I	I	I	I	I	I	I	I
Telephone Check-in		I & W	I	I	I	I & W	I	I	I	I & W	I & W
BFI	X	X				X				X	X
PROMIS-29 V2.0		X				X				X	X
CEQ (questions 1,2)		X				X				X	X
CEQ (questions 3, 4)		X									X

X = everyone

I = Baduanjin Intervention group

W = Waitlist control group

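### Non-serious adverse events are scheduled for assessment in the exercise arm only, and the protocol's statements of the adverse-event window and the control-arm calls contradict one another

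*Protocol*

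**What the plan says.** Protocol section 3 states: "The secondary objectives are to determine the effectiveness and safety of the remotely delivered Baduanjin mind-body exercise program for CRF". Section 10 lists as a secondary outcome "The number and severity of reported side effects and / or adverse events", with no restriction by arm. The Data analysis part of section 10 has endpoints analysed by intention to treat and per protocol.

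The collection rules are spread over several places:

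- **Section 10, Adverse Events Reporting and Management, AEs:** "All AEs that occur between the first intervention and the last intervention for the study must be recorded in detail".
- **Same part, serious AEs:** "All Serious Adverse Events (SAEs) occurring between consent and the last visit for the study are recorded in detail in the Adverse Events Form".
- **Same part, sources of reports:** the weekly calls ask about side effects of the exercise, instructors take daily reports, and the logbook goes to intervention participants.
- **Section 10, Endpoints:** "reported adverse events at baseline (week 0), 4 weeks, 8 weeks and 9 weeks (1 week follow-up".
- **Appendix 1:** the row "AE Assessment" carries only the code for the intervention group, in weeks 1 to 9.
- **Section 5.8, intervention group:** a final call in week 9, one week after the program ends, asks about adverse experiences.
- **Section 5.8, control-group time summary:** "Telephone weekly check-ins: approx. 5 minutes per week (40 minutes", plus a final call in week 9. The telephone row of Appendix 1 marks controls only at weeks 0, 4, 8 and 9.

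**The concern.** An AE count in one arm mixes effects of the exercise with events that would have happened anyway. Randomisation to a wait-list could supply that background rate, but only if controls are asked. Here the overlap is visible in the protocol itself. Section 6.2 lists nausea and vomiting among reported reactions to the exercise, section 2 discusses them alongside fatigue as symptoms of cancer or its treatment, and section 5.5 admits people receiving chemotherapy.

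Three things are at stake:

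- A stated secondary outcome, listed among endpoints to be analysed by intention to treat, would be collected systematically in only half of those randomised.
- Staff cannot tell from the text whether a non-serious event first reported in week 9 is to be recorded.
- Staff cannot tell how often to call controls.

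All three concern data collection. No later analysis plan can recover events that were never sought.

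**Working it through.** **1. Who is asked.** Count the entries in Appendix 1.

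- AE row: 9 entries for the intervention group (weeks 1 to 9), 0 for the wait-list group and 0 for everyone.
- Telephone row: 10 entries for the intervention group (weeks 0 to 9) and 4 for the wait-list group (weeks 0, 4, 8, 9).

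The text agrees with the AE row. The AE window is defined by first and last intervention, and section 5.8 gives controls no intervention from week 0 to week 9. No passage sets out non-serious AE collection in controls.

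**2. Over what period.** Set side by side:

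- AE recording rule (section 10): first to last intervention, so within weeks 1 to 8.
- Week 9 call (section 5.8): adverse experiences asked about after the last intervention.
- Appendix 1: weeks 1 to 9.
- Endpoints (section 10): weeks 0, 4, 8 and 9.
- Serious AEs (section 10): consent to last visit.

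For non-serious AEs, the first rule leaves out week 9 and the other three include it. The Endpoints paragraph includes week 0, while the recording rule and Appendix 1 start later.

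**3. How often controls are called.** Section 5.8: 40 minutes / 5 minutes per call = 8 weekly calls, plus the final call. Appendix 1: 4 contacts. If Appendix 1 is the operating schedule, controls have no call in weeks 1, 2, 3, 5, 6 and 7.

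**4. What the missing comparator means in numbers.** The protocol gives no background symptom rate, so take 5% to 30% as an assumption. With 20 exercisers and no effect of the exercise at all:

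- Expected participants with an event: 20 × 0.05 = 1 to 20 × 0.30 = 6.
- Chance of at least one: 1 − 0.95^20 = 0.64 to 1 − 0.70^20 = 0.999.

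Events in the exercise arm are thus likely even if the exercise is harmless, and there would be no control figure to set beside them.

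**5. The plan's own detection figure.** Section 5.3 states n = 29 for 95% confidence of detecting an event with probability 0.10. This reproduces: ln(0.05)/ln(0.90) = 28.43, rounded up to 29, and 1 − 0.90^29 = 0.953. Asked in 20 exercisers only, the chance of seeing such an event is 1 − 0.90^20 = 0.878, or 1 − 0.90^17 = 0.833 if 15% are lost (20 × 0.85 = 17). Asked in all 40 it is 1 − 0.90^40 = 0.985. The last figure applies only to events that can occur in both arms. Problems specific to the exercise can arise only in the 20 exercisers, whatever controls are asked.

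**6. What control data could show.** Approximate 95% half-width of a risk difference with 20 per arm: 1.96 × √(2p(1 − p)/20). At p = 0.10 this is 0.19 and at p = 0.30 it is 0.28. Control data would give context, not a usable test.

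**The case against.** The strongest reply is that this is a feasibility pilot. AE count and severity is one of four secondary outcomes, no between-arm test of AEs is stated, and the half-widths above show that none would be informative. Section 10 also requires severity, expectedness and causal relationship to be judged for every AE, and section 7 provides independent safety review by a non-investigator. This stands as an argument about weight. It does not remove the gap, because case-by-case causality judgement does not replace a background rate.

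Stronger readings are tempting, but the documents do not support them:

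- A reader might infer that the trial has no safety comparator at all. Serious AEs run from consent to the last visit with no restriction by arm, so the gap is confined to non-serious events.
- A reader might infer that AE recording stops at the last session. One sentence says so. The week 9 call, the week 9 entry in Appendix 1 and the week 9 endpoint say otherwise, and events open at the last intervention are followed to resolution. The finding is a contradiction, not a closed window.
- A reader might infer that every participant has current chemotherapy symptoms overlapping all the listed exercise reactions. Section 5.5 also admits people who have completed chemotherapy, and the protocol itself links only nausea and vomiting to cancer or its treatment.
- A reader might infer that unequal calls bias retention and reported fatigue. Call frequency is unequal only if Appendix 1 governs. The exercise arm is in any case offered daily Zoom contact, so unequal attention comes with the wait-list design.

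**Conclusion.** The point holds for non-serious AEs: nine scheduled assessments per exerciser against none per control, so this part of the secondary safety outcome has no randomised comparator. It also holds that the AE window is stated inconsistently in sections 5.8 and 10 and Appendix 1, and that control-arm calls are stated inconsistently in section 5.8 and Appendix 1. These counts are read directly from the protocol. The only assumption is the 5% to 30% background rate, which illustrates the consequence and is not needed for the conclusion. The primary feasibility outcomes do not depend on AE data, and capture of serious AEs is already neutral between arms. This should therefore be fixed, but it is not critical to the pilot.

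**What to change.** - In Appendix 1, mark AE assessment for both groups.
- Ask the same neutral AE question, not tied to exercise, on the same form and at the same contacts in both arms: weekly if section 5.8 governs, otherwise at least at the shared contacts in weeks 4, 8 and 9.
- Define one AE window for both arms, from randomisation to the week 9 contact. State whether the week 0 endpoint entry is a baseline record or should be dropped.
- Report AEs descriptively by allocated arm, with relatedness to the exercise shown separately.
- Reconcile section 5.8, the AE and Endpoints parts of section 10, and Appendix 1 on the window and on control-arm calls.

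**Cost.** Mainly wording, plus one question at contacts that exist under either schedule. More unrelated events will be recorded. If Appendix 1 is the operating schedule and weekly calls are chosen, 6 weeks × 20 controls = 120 extra calls. At 5 minutes each this is 600 minutes, or 10 hours. Section 9 budgets 8 × 50 = 400 hours for the research assistant who makes the calls, so the addition is 10/400 = 2.5% of that time.
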